## Introduction

Central venous pressure (CVP) measured invasively through a central venous catheter in the internal jugular vein or through a right atrial port of a pulmonary artery catheter is commonly used during liver transplant surgery. CVP measurements at the SVC-RA junction are a function of circulating blood volume, right ventricle function, intrathoracic pressure. (1) CVP measurements can also be affected by the presence of tricuspid regurgitation. Because central venous pressure measurements are determined by several factors and do not predict the response to subsequent fluid bolus administration, they are considered “static measures” and are poor indicators of fluid responsiveness. (2)

CVP measurements remain an important measurement during liver transplant surgery (3) since a rise in CVP especially during the postanhepatic phase can alert the perioperative team to worsening pulmonary artery elevations and/or a decline in RV function. (4) This in turn triggers several therapeutic interventions aimed at reducing an increasing afterload on the newly transplanted liver, which can otherwise result in disruption of liver anastomoses, increased bleeding and coagulopathy and liver failure of the transplanted liver.(5)

In spontaneously breathing patients, transthoracic echocardiographic measurements of the inferior vena caval diameter and its change with inspiration (sniff) is routinely used to estimate right atrial pressure measurements (Size <2.1 cm; collapses >50% during sniff = RAP 0–5 mm Hg; if Size > 2.1 cm; collapses >50% during sniff = 5–10 mm Hg if Size > 2.1; collapses <50% during sniff = 10–20 mm Hg. This echocardiographic measurement allows noninvasive estimation of pulmonary artery systolic pressure based on the modified Bernoulli equation (PASP=RVSP= 4v + RA pressure). (6)

Due to its intraabdominal location, the IVC is less suited for estimation of right atrial pressure during mechanical ventilation; especially that positive pressure ventilation causes a dilation of IVC diameter. (7)

Given the entirely intrathoracic location of the superior vena cava (SVC), its diameter and collapsibility with positive pressure ventilation it is a potentially attractive method of non-invasively estimating CVP. (8)

SVC diameter and collapsibility index, dynamic measures of fluid responsiveness have been successfully utilized as echocardiographic indices for fluid responsiveness in ventilated septic patients. (9) Whether SVC collapsibility is correlated with CVP measurements in liver transplant patients is not known.

**Significance:**

While most centers utilize central venous catheters or pulmonary artery catheters during liver transplant surgery, (3) there are complications associated with central invasive catheter use. (10)

If SVC collapsibility index is correlated with CVP measurements, it would allow:

- 1- Less reliance on central invasive catheter use especially in select population of liver transplant recipients especially those with normal pulmonary artery pressures and normal right ventricle function. Large bore peripheral venous catheters that allow rapid administration of fluids and blood products would substitute central venous catheter use with transesophageal monitoring of SVC diameter and collapsibility for calculation of pulmonary artery systolic pressure (PASP).
- 2- Noninvasive measurement of PASP in mechanically ventilated patients with no central venous monitoring (not just in patients undergoing liver transplantation) especially that IVC measurement in mechanically ventilated patients may be inaccurate in identifying CVP. (7) Since the SVC is entirely located intrathoracic its collapsibility with positive pressure ventilation makes it an attractive method of non-invasively estimating CVP.(8)
- 3- There are no studies that identify the changes in SVC diameter and collapsibility index during IVC cross- clamping (during the anhepatic phase of liver transplant surgery). This study will provide insight to changes in SVC diameter and collapsibility index in response to IVC crossclamping during the anhepatic phase.

**Hypothesis:**

SVC diameter and SVC collapsibility index is correlated with CVP measurement in patients undergoing liver transplant surgery (liver transplant recipients)

**Aim of the study:**

- 1- To assess the correlation of SVC diameter and SVC collapsibility index measurements obtained intraoperatively by Transesophageal echocardiography (TEE) with simultaneous CVP measurements obtained and recorded electronically ( via an automated intraoperative record keeping system) through a centrally inserted central venous catheter or a right atrial port of a pulmonary artery catheter
- 2- To identify the changes in SVC diameter and SVC collapsibility index that occur with inferior vena cava cross clamping during liver transplant cases performed using IVC cross clamping

**Inclusion criteria:**

Adult patients => 18 years of age undergoing liver transplantation surgery (cadaveric and living related)

**Exclusion criteria:**

Contraindication to Transesophageal echocardiography: Esophageal pathology (stricture, trauma, tumor, scleroderma, Mallory-Weiss tear, diverticulum), Active upper gastrointestinal bleed, perforated viscous, esophagogastrectomy, esophagectomy, recent upper gastrointestinal surgery. (11)

**Methods:**

Following RAC and IRB approval, consecutive patients undergoing liver transplant surgery will be included in the study. We will ask the IRB for informed consent waiver since both TEE and central venous monitoring are used routinely in liver transplant recipients.

Simultaneous measurements of SVC diameter, SVC collapsibility index, CVP (captured electronically through an automated record keeping system) will be recorded by experienced anesthesiologists with expertise and qualifications in Transesophageal Echocardiography. **Simultaneous cardiac output measurements (thermodilution) will also be recorded.**

Measurements of the SVC will be taken in the midesophageal bicaval view (90-110 degrees) using M-mode echocardiography, 1 to 2 cm away from the entry point into the right atrium. This technique is analogous to that recommended when measuring IVC diameter and collapsibility (7) and was previously described by Cowie et al. (8)

The maximum and minimal diameter of the SVC will be measured and recorded.

Collapsibility index of SVC, “SVC collapsibility index” which is a measure of the inspiratory decrease in SVC diameter will be determined based on the following formula

(Maximum diameter on expiration—minimum diameter on inspiration)/Maximum diameter on expiration, expressed as a percentage

Patients will be ventilated using Pressure Control Ventilation with a tidal volume of 6 to 8 ml/kg with a respiratory rate of 10-12/min and a positive end expiratory pressure of 5 to 8 cmH2O.

Measurements will be recorded during the following time periods:

- 1- Before surgical incision ( following induction of General Anesthesia and placement of invasive monitoring and TEE)
- 2- Preanhepatic phase
- 3- Anhepatic phase
- 4- Postanhepatic phase ( following reperfusion)
- 5- Following closure of the deep fascial layer of the anterior abdominal wall

Simultaneously, CVP will be recorded from the right atrial port of the pulmonary artery catheter or from the proximal port of a CVC inserted in the internal jugular vein

Patients will be placed in the supine position with pressure transducers zeroed to atmospheric pressure and located at the mid-thoracic position, half-way between the sternum and bed, as recommended in recent guidelines. (12)

### **Statistical methods**

Demographics and perioperative characteristics of this cohort will be summarized using the standard summary statistics.

We will use a linear mixed effect model with repeated measures to estimate the correlation between (1) SVC diameter and (2) SVC collapsibility index and simultaneously measured CVP across over the five measurement times, including before surgical incision, start of preanhepatic phase, start of anhepatic phase, start of postanhepatic phase, and after closure of deep fascial layer of the anterior abdominal wall (13). In the mixed model, an unstructured covariance matrix will be used to account for within-patient correlation. The significance criterion will be 0.025 for each analysis; thus 97.5% CI will be reported (i.e., 0.05/2, Bonferroni correction).

In addition, we will assess whether the correlation between SVC diameter and SVC collapsibility index and CVP differs over measurement time (time interaction) using a separate linear mixed effect model with a time interaction term. Regardless of the significance of the interaction, we will report the correlation coefficient at each of the five measurement times along with 99.5% confidence interval (i.e., 0.025/5, Bonferroni correction) for information purpose.

Secondly, we will also assess whether the correlation between SVC diameter and SVC collapsibility index and CVP differs between patients with and without normal pulmonary artery pressures and normal right ventricle function. If the above interaction exists, we will report the correlation separately.

The changes in SVC diameter and SVC collapsibility index that occur with inferior vena cava cross clamping during liver transplant will be summarized.

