#### Sample Size Considerations

With 100 patients and 5 pairs of measurement per patients we will provide enough data to adequately study the accuracy. For example, the width of our 97.5% CI for Pearson correlation will range from 0.19 to 0.15 for correlations ranging from 0.2 to 0.5, respectively, assuming a within-subject correlation of 0 (i.e., equivalent to 500 independent patients). In the other of the extreme scenario (i.e., within-subject correlation of 1), the width of our 97.5% CI for Pearson correlation will range from 0.43 to 0.34 for correlations ranging from 0.2 to 0.5, respectively. Approximately 10 liver transplant cases per month are conducted at the Cleveland Clinic main campus. Thus, a plan of 100 patients is feasible within 1 year. SAS software version 9.4 for Windows (SAS Institute, Cary, NC, USA) will be used for all analyses.

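### The tested SVC–CVP correlation, and the per-phase values beside it, cannot show whether SVC tracks CVP within a patient, and the plan does not say whether phase means are in the tested model.

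*Combined protocol and SAP*

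**What the plan says.** The Statistical methods section plans a repeated-measures linear mixed model "to estimate the correlation between (1) SVC diameter and (2) SVC collapsibility index and simultaneously measured CVP across over the five measurement times", with an unstructured covariance and a 97.5% CI for each of the two SVC measures. No fixed effects are listed for this model, and reference 13, a paper on estimating correlation with PROC MIXED, is cited for it. Time is named as a model term only for the next question, whether the correlation differs by time, which is assessed "using a separate linear mixed effect model with a time interaction term". Whatever that model shows, "we will report the correlation coefficient at each of the five measurement times along with 99.5% confidence interval"; these values are described as informational. No between-patient or within-patient correlation is defined.

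Sample Size Considerations treats the target as a single Pearson correlation. It gives CI widths for two extremes, one "assuming a within-subject correlation of 0 (i.e., equivalent to 500 independent patients" and the other a within-subject correlation of 1, where "the width of our 97.5% CI for Pearson correlation will range from 0.43 to 0.34".

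Three places elsewhere suggest that the variables may move during surgery, without giving a size or direction:
- Introduction: "a rise in CVP especially during the postanhepatic phase can alert the perioperative team".
- Significance: "This study will provide insight to changes in SVC diameter and collapsibility index in response to IVC crossclamping during the anhepatic phase".
- Aim of the study: SVC changes are to be identified "that occur with inferior vena cava cross clamping during liver transplant cases performed using IVC cross clamping", wording that leaves room for cases done without clamping.

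**The concern.** The Significance section proposes monitoring the SVC by TEE instead of using a central venous catheter in selected recipients. For that, what matters is whether the SVC measure follows CVP as it changes in one patient. A total correlation can be respectable only because patients with generally higher CVP also have generally larger SVCs, even if the SVC does not follow CVP within any of them. The reverse can also happen: good tracking within patients can be diluted by unrelated differences between patients. The per-phase correlations do not settle this, because each compares 100 different patients at one time.

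The second gap is the mean structure. If phase means are not in the tested model, movement of both variables from phase to phase becomes part of the tested value and can raise or lower it. Whether that movement counts as signal is a legitimate choice, but the plan does not state it.

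**Working it through.** **1. The plan's own widths.** Inputs from Sample Size Considerations: r = 0.2 and 0.5, 500 or 100 pairs, 97.5% CI. Fisher z interval: tanh(atanh r ± 2.2414/√(n − 3)).

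| n | r | Interval | Width | Plan |
|---|---|---|---|---|
| 500 | 0.2 | 0.102 to 0.294 | 0.192 | 0.19 |
| 500 | 0.5 | 0.421 to 0.572 | 0.151 | 0.15 |
| 100 | 0.2 | −0.025 to 0.406 | 0.430 | 0.43 |
| 100 | 0.5 | 0.311 to 0.651 | 0.340 | 0.34 |

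All four reproduce. The tested quantity is therefore best read as one total correlation.

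**2. The blend.** Assume the same ICC in both variables; the documents give none. Then total = ICC × between + (1 − ICC) × within.

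| ICC (assumed) | Between 0.6, within 0 | Between 0, within 0.6 |
|---|---|---|
| 0.2 | 0.2 × 0.6 = 0.12 | 0.8 × 0.6 = 0.48 |
| 0.5 | 0.5 × 0.6 = 0.30 | 0.5 × 0.6 = 0.30 |
| 0.8 | 0.8 × 0.6 = 0.48 | 0.2 × 0.6 = 0.12 |

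At ICC 0.5, opposite truths give the same total. Under this model each single-phase correlation has the same expectation, so the five planned values cannot separate the two either.

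**3. Phase means left out.** Assume equal SDs and a shift of d SD in one of five phases, in all cases. The variance of the phase means is d² × (1/5) × (4/5) = 0.16d².
- Both variables move together, no association within any phase: d = 1 gives 0.16/1.16 = 0.138; d = 0.5 gives 0.04/1.04 = 0.038.
- Opposite directions, true r = 0.2, d = 1: (0.2 − 0.16)/1.16 = 0.034.
- Only one variable moves, d = 1: a true zero stays zero, and 0.5 becomes 0.5/√1.16 = 0.46.

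In the same-direction case with no association the five per-phase correlations average 0.00, so the planned output would show the gap of 0.14.

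**4. Mixed clamping.** Let a share p of cases be clamped (not given in the documents), with a 1 SD shift of both variables in the anhepatic phase. Mixing alone gives an anhepatic correlation of p(1 − p)/(1 + p(1 − p)). That is 0.25/1.25 = 0.20 at p = 0.5, the maximum, and 0.09/1.09 = 0.08 at 10% or 90%. After plain phase means the total keeps 0.05/1.05 = 0.048 at p = 0.5, and 0.018/1.018 = 0.018 at 10% or 90%.

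**5. Precision of the added values at r = 0.3.** Within patient there are 100 × (5 − 1) = 400 degrees of freedom. The half-width on the z scale is 2.2414/√398 = 0.112, giving 0.195 to 0.399, a width of 0.20. Between patient, simulation of 100 patients × 5 times gave widths of 0.82, 0.48 and 0.41 at ICC 0.2, 0.5 and 0.8.

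**The case against.** - **The blend is not an error.** The Hypothesis section asks only whether the measures are correlated, and a total correlation answers that. This stands. The point is an addition that serves the stated use, not a correction of the test.
- **Phase means may be intended.** A reader might infer that the plan leaves them out. The documents do not support that: the text is silent, and the cited reference, which cannot be consulted here, may set the mean structure. If phase means are included, step 3 falls away and the blend remains.
- **The per-phase correlations already guard against a common shift.** They largely do. Mixed clamping weakens the guard, but step 4 shows a small effect unless the mix is near half and the shift near 1 SD.
- **A reader might infer a badly inflated error rate.** In a simulation with no association and a same-direction 1 SD shift, the 97.5% CI excluded zero in 78%, 59% and 39% of trials at ICC 0.2, 0.5 and 0.8. At 0.5 SD this fell to 8%, 7% and 5%. These are not the plan's error rates. No section states a joint shift in one phase: the CVP rise is mentioned especially after the anhepatic phase, the SVC change with anhepatic clamping. The simulation used a pooled correlation with a bootstrap, not the planned mixed model. And if the unadjusted total is the target, 0.138 is its true value and excluding zero is no mistake.
- **Phase movement may be the signal.** CVP is valued in the Introduction for showing change during surgery. That argues for reporting the total both ways, not for moving the 0.025 test to an adjusted value.

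**Conclusion.** The point holds as a cheap improvement of minor to moderate weight. Neither the tested total nor the per-phase values can show whether SVC tracks CVP within a patient, although the planned 100 × 5 data can. That rests on an identity; only the illustrative ICC and correlations are assumed. The unstated mean structure is a gap in specification. Its possible effect on a true zero, about 0.14 for a 1 SD same-direction shift and 0.04 for 0.5 SD, rests on assumed shifts that the documents do not establish, and the per-phase output would largely expose a shift common to all cases. The findings do not show that the primary test is invalid or that the sample size is wrong.

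**What to change.** Keep the total correlation, its test at 0.025 and the five per-phase values as planned. Add to the SAP:

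1. A statement of whether phase is a fixed effect for both CVP and the SVC measure in the tested model.
2. The total correlation both with and without phase means, saying which one is tested.
3. The within-patient and between-patient correlations with 97.5% CIs, from the same bivariate mixed model. Write its covariance out so that the patient-level and same-time parts can be separated.

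Optional sensitivity analyses are phase-by-clamping means, if both clamped and unclamped cases occur, and patient-level bootstrap intervals, since model-based standard errors from a simple two-level structure can be too small under serial correlation.

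The cost is a few sentences and a little code. No new patients or measurements are needed, and Aim 2 already requires clamping status. The downsides are a wide between-patient interval (about 0.4 to 0.8 at r = 0.3) and a within-patient value that may be less favourable than the headline.

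### The plan correlates levels of the SVC measures with levels of CVP but has no output showing whether they move with CVP within a patient, although the protocol values CVP for the warning given by a rise

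*Combined protocol and SAP*

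**What the plan says.** The Introduction gives the reason for monitoring CVP: "a rise in CVP especially during the postanhepatic phase can alert the perioperative team to worsening pulmonary artery elevations". It adds that this leads to interventions. The Significance section then opens its list of benefits with "If SVC collapsibility index is correlated with CVP measurements, it would allow", and the first benefit is "Less reliance on central invasive catheter use especially in select population of liver transplant recipients". Correlation is the only condition named there.

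Statistical methods plans the following outputs:
- For each SVC measure, a correlation with CVP over the five times: "We will use a linear mixed effect model with repeated measures to estimate the correlation between (1) SVC diameter and (2) SVC collapsibility index". The error rate is split between the two measures: "The significance criterion will be 0.025 for each analysis; thus 97.5% CI will be reported".
- A test of whether the correlation differs over time, and, for information, "we will report the correlation coefficient at each of the five measurement times along with 99.5% confidence interval".
- A comparison of the correlation by pulmonary artery pressure and right ventricular function status.
- A summary of the changes in the SVC measures with IVC cross-clamping.

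The last two of the five readings are at "start of postanhepatic phase, and after closure of deep fascial layer of the anterior abdominal wall". No CVP rise is defined, and no output sets a change in an SVC measure against the change in CVP in the same patient.

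**The concern.** The warning described in the Introduction is a change over time in one patient. The planned correlations mainly answer a different question: whether patients with higher CVP also have a wider or less collapsible SVC. Body size, cardiac function or baseline volume status could produce such an association even if the SVC measures barely responded when CVP moved.

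What is at stake is the conclusion. A significant correlation could be reported as support for less catheter use with no evidence that the proposed replacement follows CVP within a patient. The one planned summary of change does not fill the gap. It covers cross-clamping rather than the postanhepatic phase, and it describes the SVC measures alone.

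**Working it through.** **1. The plan's own figure.** Inputs from Sample Size Considerations: 100 patients, 5 pairs each, 97.5% CI, correlations of 0.2 and 0.5, and within-subject correlation of 0 (effective n = 500) or 1 (effective n = 100). Fisher interval: tanh(atanh(r) ± 2.2414/√(n − 3)).

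| Effective n | r | 97.5% CI | Width | Plan states |
|---|---|---|---|---|
| 500 | 0.2 | 0.10 to 0.29 | 0.192 | 0.19 |
| 500 | 0.5 | 0.42 to 0.57 | 0.151 | 0.15 |
| 100 | 0.2 | −0.02 to 0.41 | 0.430 | 0.43 |
| 100 | 0.5 | 0.31 to 0.65 | 0.340 | 0.34 |

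All four widths are reproduced. The arithmetic is sound, but it concerns only the precision of a level correlation.

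**2. What a level correlation can hide.** Write each reading as a patient component plus an occasion component. Let s be the share of variance between patients, taken as equal for CVP and the SVC measure, with equal variances at each time and independent occasion components. Then:
- level correlation = s × ρ(between) + (1 − s) × ρ(within);
- the difference between two times removes the patient component, so change correlation = ρ(within).

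The documents give no value for s, so these are assumed cases:
- s = 0.7, ρ(between) = 0.7, ρ(within) = 0: level 0.7 × 0.7 + 0.3 × 0 = **0.49**; change **0**. A simulation of 400,000 patients gave 0.49 and 0.00.
- s = 0.7, ρ(between) = 0.7, ρ(within) = 0.3: level 0.49 + 0.09 = 0.58; change 0.3.
- s = 0.7, ρ(between) = ρ(within) = 0.5: level 0.35 + 0.15 = **0.50**; change **0.5**.

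The first and third cases give almost the same level correlation, near the top of the plan's 0.2 to 0.5 range, with very different tracking. The correlation at each time cannot separate them.

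**3. Illustration of wrong-direction movement.** Take changes as bivariate normal. Centred at zero, the share of CVP rises in which the SVC measure moves against its expected direction is arccos(r)/π, where r is the change correlation: 44% at 0.2 and 33% at 0.5. Other assumed mean shifts, with the SVC measure signed so that a positive change is the expected response to a CVP rise:

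| Mean shift, CVP / SVC (SD) | r = 0.2 | r = 0.5 |
|---|---|---|
| +0.5 / +0.5 | 27% | 21% |
| +1 / +1 | 14% | 11% |
| −0.5 / −0.5 | 61% | 47% |
| +1 / −0.5 | 67% | 65% |

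The spread, about 11% to 67%, is driven largely by mean shifts on which the documents are silent.

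**4. Precision of the missing analysis.** With 100 patients and one change each, the 97.5% CI for a change-on-change correlation is −0.02 to 0.41 at 0.2 and 0.31 to 0.65 at 0.5. If 25 patients had a rise and the SVC measure followed in 13, the proportion would be 52% (Wilson 95% CI 34% to 70%).

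**The case against.** The strongest reply is that the hypothesis and the first aim concern correlation, and no aim concerns detecting rises. The Significance section is not a decision rule. The substitution it describes uses SVC monitoring to calculate pulmonary artery systolic pressure, which is an estimate of level. It singles out recipients with normal pulmonary pressures and right ventricular function, and the plan already examines the correlation by that status. CVP is measured in every study patient, so the study itself withholds no warning. The plan also reports a correlation at the postanhepatic reading, and the correlation over five times carries some within-patient information.

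All of this is fair, and it limits the point to what may be concluded from the results. It does not close the gap. The postanhepatic correlation compares different patients at one moment, and the overall correlation mixes the two sources with no separate within-patient estimate planned.

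A reader might infer more than the documents support:
- *That any correlation from 0.2 to 0.5 would meet the hypothesis.* At effective n = 100, significance at 0.025 needs |r| of about 0.22, and the interval at 0.2 includes zero. The plan offers these values as examples of CI width, not as success criteria.
- *That a known share of rises would be missed.* The plan's values are level correlations and do not determine change correlations. It defines no rise and gives no rate of rises.
- *That Methods and Statistical methods disagree on the postanhepatic reading.* Methods names the period and explains it as following reperfusion; Statistical methods places the reading at its start. The two are compatible.

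**Conclusion.** The concern holds in limited form. The protocol values CVP for the alert given by a rise and names correlation as the only condition for less catheter reliance, yet plans no output on within-patient tracking. A significant level correlation, which may be negative for the collapsibility index, is compatible with none: 0.49 for levels beside 0 for changes, under an assumed 70% between-patient share. This shows what is possible and does not predict the result. The wrong-direction percentages are illustrative only. The sample size calculation is correct for what it covers. This is an inexpensive improvement that bounds the clinical claim, and the correlation analysis itself can stand.

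**What to change.** **Statistical methods.** Add a descriptive analysis, from the five pairs already collected, of within-patient change in SVC diameter and collapsibility index against change in CVP:
- Intervals: postanhepatic to closure, and anhepatic to postanhepatic. Show the second separately for cases with and without IVC cross-clamping, because clamp release may itself shift the measures.
- Report the change-on-change correlation with its CI.
- Report direction concordance for both rises and falls in CVP, so that missed rises and false alarms are both visible. State the expected direction for each SVC measure in advance. Exclude changes smaller than a limit that the investigators fix before data review.
- State that a rise between the postanhepatic and closure readings that has resolved by closure is not captured. The documents do not say whether CVP between readings becomes study data. If the electronic record retains it, report how often the highest postanhepatic CVP fell outside the paired readings.

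**Significance.** Make the statement on less catheter reliance conditional on this tracking result as well as on the correlation.

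**Cost.** SAP wording and one table, with no new patients or TEE readings. The downsides are modest precision with 100 patients and a less favourable clinical claim if tracking is poor.

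### Optional improvement: Holm's step-down in place of plain Bonferroni for the two primary correlations keeps the 5% familywise error and adds 0 to about 12 points to the chance of establishing both

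*Combined protocol and SAP*

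**What the plan says.** The Hypothesis section names both measures: "SVC diameter and SVC collapsibility index is correlated with CVP measurement in patients undergoing liver transplant surgery". The Statistical methods section uses a mixed model "to estimate the correlation between (1) SVC diameter and (2) SVC collapsibility index and simultaneously measured CVP", which makes two primary analyses. It then sets the criterion: "The significance criterion will be 0.025 for each analysis; thus 97.5% CI will be reported (i.e., 0.05/2, Bonferroni correction". Each measure is held to 0.025 whatever the other shows, and no step-down rule is mentioned. The per-time-point results inherit the 0.025 split, as a "99.5% confidence interval (i.e., 0.025/5, Bonferroni correction) for information purpose".

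Sample Size Considerations gives no power. It is built on the width of the 97.5% interval "With 100 patients and 5 pairs of measurement per patients", between two extremes. At one extreme the data count as 500 independent pairs, and "the width of our 97.5% CI for Pearson correlation will range from 0.19 to 0.15 for correlations ranging from 0.2 to 0.5, respectively". At the other they count as 100, and the width "will range from 0.43 to 0.34 for correlations ranging from 0.2 to 0.5, respectively".

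No section says whether the hypothesis needs one significant correlation or both.

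**The concern.** With two tests, Bonferroni requires p below 0.025 from each. Holm requires p below 0.025 from the smaller p-value and, only if that passes, p below 0.05 from the other. Holm controls the familywise error at 5% under any dependence between the tests, and it rejects everything that Bonferroni rejects.

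The second measure can therefore miss significance under the plan, with p between 0.025 and 0.05, when another rule with the same error guarantee would have declared it. At stake is the chance of ending the study with both measures established when both are truly correlated with CVP. The validity of either test is not in question.

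**Working it through.** **Inputs from the documents.** Two tests at 0.025; effective size from 100 to 500; true correlations from 0.2 to 0.5.

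**Assumptions not in the documents.** Two-sided tests (implied, because two-sided 97.5% intervals reproduce the stated widths); Fisher z statistics treated as bivariate normal; correlation rho between the two statistics, each oriented in its expected direction, from 0 to 0.8. A non-zero rho is likely because the index is computed from the diameters. Below, r is the size of the true correlation, whatever its sign.

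**Step 1: the plan's own figures.** The interval is tanh(atanh(r) ± 2.241/√(n−3)).

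| n | r | Computed width | Stated |
|---|---|---|---|
| 500 | 0.2 | 0.1925 | 0.19 |
| 500 | 0.5 | 0.1507 | 0.15 |
| 100 | 0.2 | 0.4304 | 0.43 |
| 100 | 0.5 | 0.3398 | 0.34 |

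All four reproduce, and 0.025 + 0.025 = 0.05.

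**Step 2: error control.** Holm's first step is the same 0.025 test. Simulated familywise error with both nulls true is 4.96%, 4.65% and 4.02% at rho = 0, 0.5 and 0.8.

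**Step 3: chance of establishing both.** Each statistic has mean atanh(r)·√(n−3). Bonferroni establishes both if both |Z| exceed 2.241. Holm does so if the larger exceeds 2.241 and the smaller exceeds 1.960.

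*One strong, one weak (n = 100, r = 0.5 and 0.2).* The strong measure passes almost surely, so the weak one decides. Its mean is 0.2027 × √97 = 1.997. P(Z > 2.241) = 0.403 and P(Z > 1.960) = 0.515, so 40% becomes just under 52%. Rho hardly matters here.

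*Both at 0.25 (n = 100), rho = 0.* The mean is 0.2554 × √97 = 2.516. Power per test is 0.6080 at 0.025 and 0.7107 at 0.05. Bonferroni: 0.6080² = 0.370. Holm: 0.7107² − (0.7107 − 0.6080)² = 0.495. The gain is 12.5 points. With rho from 0.3 to 0.6, 42–47% becomes 53–57%.

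**Step 4: across the range.**

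| Effective n | r | Bonferroni | Holm | rho |
|---|---|---|---|---|
| 100 | 0.20, 0.20 | 16–30% | 25–39% | 0–0.8 |
| 100 | 0.30, 0.20 | 35–38% | 46–49% | 0.3–0.6 |
| 100 | 0.30, 0.30 | 62–72% | 74–79% | 0–0.8 |
| 100 | 0.40, 0.40 | 94.7–95.8% | 97.3–97.6% | 0–0.8 |
| 100 | 0.50, 0.50 | 99.8–99.9% | 99.9% | 0–0.8 |
| 167 | 0.20, 0.20 | 45–50% | 57–61% | 0.3–0.6 |
| 200 | 0.50, 0.20 | 73% | 81% | any |
| 300 | 0.20, 0.20 | 80–85% | 88–90% | 0–0.8 |
| 500 | 0.20, 0.20 | 97.7–98.2% | 99.0% | 0–0.8 |

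The size 167 is 500/(1 + 4 × 0.5). That formula returns the plan's 500 and 100 at within-subject correlations of 0 and 1; the value 0.5 is an assumption.

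The gain fades quickly once the weaker correlation rises. With both at 0.3 it is 8 to 11 points at n = 100 but only 4 to 5 at n = 150.

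**Step 5: chance of establishing at least one.** Both rules require the smaller p-value to be below 0.025, so the gain is exactly zero.

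**The case against.** The study is planned for estimation. It is sized on interval width, and the criterion and the interval are deliberately tied together. Holm adds a rejection only when the second p-value lies between 0.025 and 0.05, and in exactly those cases that measure's planned 97.5% interval includes zero. Bonferroni therefore does buy something: simple simultaneous intervals that always agree with the tests. This stands, and it is the real price of the change. It does not remove the case for Holm, because the section also sets an explicit significance criterion, so claims will rest on tests as well as intervals.

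A reader might infer a general gain of about 10 points. The plan's range does not support that. On an even grid over that range, with equal correlations and rho assumed at 0.45, the mean gain is about 1.5 points, and it is below 1 point in roughly three quarters of the cells. An even grid is not a forecast, and equal correlations understate the gain when one measure is strong and the other weak, but the large gains do sit in one corner.

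A reader might also infer that the hypothesis requires both correlations to be shown. The text names both but sets no such rule. If both were required, no adjustment would be needed: each at 0.05 gives 26.5% at n = 100, r = 0.2, rho = 0, against 25.2% with Holm and 16.3% with Bonferroni. The planned correction implies that each measure may be claimed separately, and Holm suits that reading.

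Finally, whether a correlation of 0.2 has p = 0.02 or 0.03 says little about replacing invasive CVP monitoring. That is fair, and it limits the importance of the point.

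**Conclusion.** This is an available efficiency gain. Bonferroni at 0.025 per test is valid, prespecified and consistent with the stated interval widths, so the documents do not support calling it a flaw.

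Holm at the same 5% familywise error adds 0 to about 12 points to the chance of establishing both measures within the plan's range. The gain is about 9 to 12 points when at least one correlation is weak (near 0.2, or up to about 0.3 when the effective size is close to 100) and the effective size is about 100 to 170. It is about 1 point or less at 500 and about 2.5 points or less when both correlations are 0.4 or more. The sizes rest on the normal approximation and the assumed correlation between the statistics. Holm's error control and its never rejecting less rest on neither. Severity: optional.

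**What to change.** Before analysis, replace the fixed 0.025 criterion in Statistical methods with: *Holm step-down over the two primary tests, familywise alpha 0.05.* Keep the 97.5% intervals for estimation; they remain valid simultaneous intervals, and the widths in Sample Size Considerations do not change. Leave the 99.5% per-time-point intervals as they are. Report Holm-adjusted p-values: twice the smaller p-value (capped at 1) and, for the other measure, the larger of that value and its own p-value, each compared with 0.05. State that the Holm test governs the significance claim.

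The cost is one or two sentences, with no extra patients or measurements. The report must also explain any measure that is significant by Holm while its 97.5% interval includes zero. If the sponsor values test–interval agreement above the possible gain, keeping Bonferroni is defensible.
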